## PROTOCOL SYNOPSIS

Unique Identifier	HO-16-17264
Abbreviated Title	Qualitative research to categorize nasal polyps
GSK Product	Mepolizumab
Rationale	
GlaxoSmithKline (GSK) is embarking on a clinical program to assess treatment of severe, recurrent nasal polyps with an anti-interleukin-5 (anti-IL5) (mepolizumab). Patient symptomatic endpoints will form the basis for the assessment of treatment benefit of nasal polyp therapies. Currently, there is a lack of published qualitative data regarding nasal polyps to understand the symptoms (specific symptoms, duration, frequency, severity) or health-related quality of life (HRQoL) impacts for patients, as well as the patient decision-making process in electing for surgery and their pre- and post-surgical experience to treat nasal polyps. In line with regulatory requirements, the patient experience of nasal polyps will need to be characterized. Additionally, there is a requirement to evaluate existing symptomatic endpoints with respect to relevance and comprehensiveness within this population to inform GSK's clinical outcome assessment (COA) strategy for this trial. To address this unmet need GSK would like to conduct a qualitative research study with adult patients with nasal polyps to explore the disease experience from the patient perspective and to debrief existing symptomatic PROs (including overall and single item VAS's and the SNOT-22), via patient interviews and real-time data capture. This protocol details the methods and procedures that will be used in the conduct of this study.

Objectives (Primary, Secondary)	
Primary To explore the symptom, impact and surgery experience of patients with severe, recurrent nasal polyps and obtain patient feedback regarding the adequacy of the SNOT-22 and GSK VAS assessments (in terms of relevance and comprehensiveness) in assessing disease experience in nasal polyps.
 
Secondary Combined concept elicitation (CE) and cognitive debriefing (CD) interviews Concept elicitation objectives:

	
To identify through open-ended questioning the concepts that are important to patients with severe, recurrent, nasal polyps, who have been treated with surgery and the language they use to describe their disease experience. The main areas of exploration will be the symptoms with particular attention paid to the frequency, severity, duration and bother of each symptom, patients' surgical decision-making and surgical/treatment experience and the functional and HRQoL impact experienced by patients.
 
Cognitive debriefing objectives:
 
To cognitively test and explore the content and face validity of existing PRO instruments (single item VAS and SNOT-22) via assessment of the relevance and appropriateness of the items included in the instruments and the participants' ability to read, and consistently understand the instrument item wording, instructions, response option and recall period.
 
Real-time data capture app
 
To explore the patient experience of the symptoms, HRQoL impacts and treatment of nasal polyps and any day-to-day variability that exists in these experiences in 'real time' using smartphone/tablet app based technology.

Study Design	
This is a cross-sectional qualitative study comprising the conduct of semi-structured combined CE and CD telephone interviews (each 120 minutes in duration) with US (n=20) and German (n=10) adults with severe, recurrent nasal polyps. The combined CE and CD interviews aim to investigate the patient experience of nasal polyps, and the relevance and understanding of existing PRO instruments (e.g. VAS and SNOT-22). In addition to the interview, the study includes a real-time data capture task conducted with 10 of the 20 US participants over a 10-day period using smartphone/tablet app-based technology. Five of the ten participants (50%) will take part in the app task prior to their interview and the remaining five participants (50%) will take part in the app task following their interview.
 
This study will be conducted by Adelphi Values, an independent research agency specializing in health outcomes research, on behalf of GSK.

Study Population and Sampling Methods	
A sample of 20 US-English speaking patients and 10 German patients will be recruited, giving a collective sample of 30 patients. Recruitment will be facilitated by third-party vendors in

both US and Germany (MedQuest Global in US and Zeste in Germany). A purposive approach to sampling using recruitment quotas outlined in section 3.2.2 in Table 1 and Table 2 will be employed to ensure that patients with a broad range of demographic and clinical characteristics are recruited.

#### **Inclusion criteria**

To participate in the interview aspect of this study, patients must meet the following criteria:

- Participant has a clinical diagnosis of **bilateral nasal polyps** as diagnosed by endoscopy or CT scan;
- Participant is aged 18 or over;
- Participant has severe nasal polyps symptoms defined as an patient-reported nasal obstruction VAS score of >5 (see Appendix 1);
- Participant has had at least **one previous surgery in the past ten years** for the **removal of nasal polyps**. Surgery in this case is defined as any procedure involving instruments with resulting incision and removal of polyp tissue from the nasal cavity (polypectomy);
- Participant is currently an eligible candidate for polypectomy defined by:  
An overall patient-reported VAS symptom score of >7.(**Appendix 2**), **AND**

An endoscopic bilateral nasal polyp score of at least 5 out of a maximum score of 8 (with a minimum score of 2 in each nasal cavity). (

Appendix 3);

- Participant has symptoms consistent with chronic rhinosinusitis;
- Participant is currently receiving intranasal corticosteroids for the management of their nasal polyps;
- Participant is willing to participate in the study and provide informed consent;
- Participant is an English speaker and is able to read, write and fully understand the English language;
- Participant is willing to and able to attend and participate in a 120-minute interview to discuss their experiences of nasal polyps and obtain their feedback on several symptom/impact questionnaires.

In addition to meeting the interview criteria, those participants invited to take part in the real-time data capture will also be required to meet the following criteria:

- Participant owns/or has access to either a smartphone (iOS

	
or android) or tablet which has video, audio/microphone and photographic capabilities and access to either the Apple app store or google play store to download the app;
 
 
Participant is willing and able to take part in the real-time data application task and respond to a series of questions/tasks fielded to them via the application over the course of 10 days;
 
 
AND
 
Is willing to respond to some brief questions following the real-time data capture task about their experience of using the app and completing the tasks, either during their interview or in a 5-10 minute telephone call following completion of the task.
 
 
Participant has stated that they would feel comfortable recording short videos of themselves and providing audio commentary in response to questions/tasks.
 
 
Exclusion criteria Patients will not be eligible to participate in the study if they meet any of the following criteria:
 
 
Participant has received oral or injectable systemic corticosteroids in the last 4 weeks (28 days) for the management of their nasal polyps
 
Participant has a diagnosis of cystic fibrosis;
 
Participant has a diagnosis of eosinophilic granulomatosis with polyangitis (also known as Churg Strauss syndrome), Young's, Kartagener's or dyskinetic ciliary syndromes;
 
Participant has a diagnosis of antrochoanal polyps;
 
Participant has a diagnosis of nasal septal deviation occluding one nostril;
 
Participant has had acute sinusitis or upper respiratory tract infection in the last two weeks;
 
Participant has ongoing rhinitis medicamentosa (rebound or chemical induced rhinitis);
 
Participant has had an asthma exacerbation requiring admission to hospital in the last four weeks;
 
Participant is currently or has previously taken part in a clinical trial for nasal polyps;
 
Participant is unwilling or unable to comply with the requirements of the study or has a physical or mental condition or learning difficulties that, in the opinion of the physician, may affect the participant's ability to participate in the study, the responses he/she might provide or their ability to provide consent.
 

--	---


Data Source
	
This study will consist of combined concept elicitation and cognitive debriefing interviews, which will last for 120 minutes in total. All participants (20 participants from the US and 10 participants from Germany) will all complete these interviews. Ten of the 20 US participants (50%) will also complete a 10-day real-time data capture app task and provide feedback about their experience of completing this task.
 
No endpoints are specified or feature as part of this study.

Data Analysis Methods
	
Descriptive socio-demographic and clinical characteristics  Socio-demographic and clinical characteristics for participant collected from the demographics form and CRF respectively will be summarized using descriptive statistics (e.g. n vales, means, ranges, percentages etc. where relevant).
 
Analysis of interviews  All interviews will be audio-recorded, and along with audio real-time data capture app task responses, transcribed/translated verbatim. Transcripts will be analyzed using thematic analysis methods and qualitatively coded using Atlas.Ti software. The Adelphi Values project team will create the initial code list, and each transcript would be assessed and participant comments that pertain to the main research questions would be highlighted. The code list will be updated iteratively during the coding process. The CE interview data will be analyzed in accordance with the principle of conceptual saturation as fully outlined in section 4.
 
Descriptive statistics for the SNOT-22 and visual analogue scales  The data collected from the SNOT-22 and visual analogue scales during the CD interview will be scored by Adelphi Values and summarized using descriptive statistics (e.g., n values, mean scores, ranges and percentages). Information relating to the distribution of responses will be summarized in addition to any missing data. The data will be presented in tabular or graphical format, whichever is deemed most appropriate at the time of reporting the findings.
 
Real-time data capture analysis

	
Responses to the real-time data capture data will be collected using a variety of methodologies (e.g., video, audio, text and photographic responses with captions). For audio responses these will be transcribed.
 
Participants' responses to questions/tasks in the real-time data capture activity and post-activity questions administered via telephone will be analyzed in the same way using Atlas.Ti for the qualitative interviews as outlined above. Video, free text photographic and transcribed audio responses will be entered into Atlas Ti and assigned codes in the same manner as the verbatim interview transcripts to tag/code what their content conveys. For any questions/tasks fielded to participants as part of the app with multiple choice or numerical responses options, descriptive analysis of these items will be performed and reported (e.g. mean item score, ranges etc.).
 
The interview and app task results will be used to inform the further development of a conceptual model for nasal polyps, previously constructed based on literature review activity only. The qualitative analysis will also be used help summarize the content validity of the reviewed PRO instruments and their suitability for use with patients with nasal polyps.

Sample Size and Power
	
Where the goal of qualitative research is to provide comprehensive understanding of complex phenomena (e.g. the holistic experience disease from the patient/caregiver perspective), it is recommended that sample sizes are determined based on the concept of 'conceptual saturation' where no new concepts are identified with repeated data collection. Past research and experience suggests that conceptual saturation can typically be achieved in as few as 12 individual interviews in a relatively homogenous population. Taking the above into account, a total of 20 participants from the US and a total of 10 from Germany will be interviewed (total sample= 30).

Limitations
	
As the study has been designed using best practice methodology advocated by the Food and Drug Administration for exploratory qualitative studies used to support clinical measurement strategies, the foreseen risk/limitations of the study are minimal but include the following:

	

• Selection of participants: potential bias is always possible when selecting interviewees; however, as outlined in sections 3.2.1 and 3.2.2 eligibility criteria and recruitment quotas will be employed to ensure the participant sample is as diverse and representative as possible given the overall study size (n=30).

• Generalizability of data: The participant sample (n=30) is relatively small as the planned research is primarily exploratory in nature. The sample size is typical of qualitative studies conducted in this context. Nevertheless, the findings obtained from the participant interviews cannot be extrapolated or generalized to the wider population with nasal polyps; however, they will be relevant to GSK target nasal polyp population for their planned Phase III clinical trial.

• Real-time data capture: The eligibility criteria for the real-time data capture task and information included within the consent form (Appendix 5) will aim to ensure that those participants who take part in this activity are willing to take part over a period of ten days and that they would feel comfortable in providing responses using a variety of methods including video, audio, photographic and/or free text responses. As this methodology is exploratory and ethnographic in nature the quality of completion and the comprehensiveness of participant responses cannot be guaranteed. This said however, the participants will be contactable both via the app and also via email and/or telephone during the completion of the app task and as such the project researchers will endeavor to encourage the completion of all task in as thorough manner as possible (e.g. provide reminders to participants to complete their task or probes/examples if they are unsure of how to respond to a task/question).

• Conceptual saturation: Whilst conceptual saturation can typically be achieved in a sample of 12 in a relatively homogenous population, a potential limitation of the study is that conceptual saturation is not achieved across the 20 interviews. Should conceptual saturation not be achieved, discussion will be held with GSK to determine whether additional interviews should be conducted in

--	--

	order to achieve saturation.
--	------------------------------

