### **Real-time data capture**

All 20 US patients will be invited to take part in an app-based real world data capture activity. It is anticipated that of the 20 interview participants, a sub-set of ten will meet the inclusion criteria for this task. Five of the ten participants (50%) will take part in the app task prior to their interview and the remaining five participants (50%) will take part in the app task following their interview. Eligible participants will receive instruction and supporting documentation on how to download and access the application via their smartphone or tablet. Participants will be required to take part in the real-time data capture exercise over the course of 10 days and during this time a series of approximately 10 questions/tasks will be fielded to participants via the application to explore the experience of the symptoms, HRQoL impacts and treatment of nasal polyps and any day-to-day variability that exists these experiences in 'real time'. Some questions/tasks may be issued daily over the 10 days and others may be issued once. Examples of the types of questions that might be asked to participants via the application are documented in Appendix 9. Each task will take no longer than 5-10 minutes to complete and participants will be able to provide responses to the questions/tasks fielded to them using a variety of methodologies including video, audio, text and photographic responses.

Once recorded, the participants can submit their responses via Wi-Fi or 3/4G and they will become immediately viewable on a response dashboard for the study researchers to track and analyses. The AV research team would be able to interact with participants via the dashboard (e.g. add new tasks, send reminders to complete a task), monitor compliance and review and run reports on received responses to questions/tasks. All data from the dashboard would be downloaded and stored by Adelphi Values. As part of this process any video or photographic data whereby the participant's face was visible would be blurred/redacted.

Germany participants will not be invited to take part in the real-time data capture app task.

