### **Real-time data capture analysis**

Responses to the real-time data capture data will be collected using a variety of methodologies (e.g., video, audio, text and photographic responses with captions). For audio responses these will be transcribed.

Participants responses to questions/tasks in the real-time data capture activity will be analyzed in the same way using Atlas.Ti for the qualitative interviews as outlined above. Video, free text photographic and transcribed audio responses will be entered into Atlas.Ti and assigned codes in the same manner as the verbatim transcripts to tag/code

what their content conveys. For any questions/tasks fielded to participants as part of the app with multiple choice or numerical responses options, descriptive analysis of these items will be performed and reported (e.g. mean item score, ranges etc.). For those participants who complete the app task after their interview, they will answer a series of questions via telephone about their experience of this activity. This data would also be audio-recorded, transcribed verbatim and analyzed in the same way as the interview and app task data.

The interview and app task results will be used to inform the further development of a conceptual model for nasal polyps, previously constructed based on literature review activity only. The qualitative analysis will also be used help summarize the content validity of the reviewed PRO instruments and their suitability for use with patients with nasal polyps.

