### The role of the interviewer is to **inquire** and **support**:

Do not give your own point of view

Be patient and accept silence during open-ended questioning to make sure the patient has time to think about her/his response

Help the patient stick to the topics intended in the guide (but not necessarily in the order presented in the guide)

Help the patient avoid repeating himself or herself

Help the patient cross-reference and make connections that they would not do spontaneously

Ask the patient to clarify any comments that you are not certain you understood and for the benefit of the recording

Ask the patient to explain any vague reference or comment that is pertinent to the research question

**Most importantly:** avoid biasing or leading the patient

**As much as possible your questions should be open-ended and general rather than specific – use suggested probes to follow-up on topics of interest if not adequately discussed in response to the open questions.**

**It is very important that you do not lead the patient with your questions or remarks.** Ask all questions in as open-ended a manner as possible; take care not to bias the patient's response one way or the other. Below for most questions, we have provided a number of possible probes that should help the patient explain his or her thinking when s/he is talking about the topics of interest. These probes are

ADELPHI VALUES

**optional** and do not have to be asked if, when asked the initial question, the patient provides a fully elaborated response and addresses the topics noted in the probes. The probes are only provided for use when the patient finds it difficult to answer your questions, if s/he is reluctant to speak at length about experiences or if key topics of interest have not been elicited spontaneously. You may have to invent your own probes or reword the probes indicated in the interview guide; this is fine. As a fully trained and experienced interviewer we rely on your judgment as to when more information is required from the patient and for you to probe as appropriate.

POSSIBLE NON-LEADING PROBES MIGHT INCLUDE:

- Can you describe exactly how that feels?
- Tell me more about that.
- How does that affect you?
- Can you talk more about \_\_\_\_\_?
- How often does that happen?
- How long does that last?
- Is there anything that makes it better or worse?

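### App participants may be given researcher probes or examples with no non-leading rule and no stated record of email or telephone prompts, so supplied content could be coded as the patient's own

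*Combined protocol and SAP*

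**What the plan says.** The real-time data capture item under Limitations in the synopsis, repeated in section 5, concedes that full and careful app responses cannot be guaranteed. As mitigation it says "the participants will be contactable both via the app and also via email and/or telephone" during the task, and that researchers will encourage thorough completion. The means it gives are to "provide reminders to participants to complete their task or probes/examples if they are unsure of how to respond to a task/question".

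Section 3.3 (Real-time data capture) adds that the research team can use the dashboard to "add new tasks, send reminders to complete a task", and that all dashboard data will be downloaded and stored.

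On analysis, the synopsis says app responses are "assigned codes in the same manner as the verbatim interview transcripts"; section 4 likewise has them "assigned codes in the same manner as the verbatim transcripts". On use, both say: "The interview and app task results will be used to inform the further development of a conceptual model for nasal polyps".

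The interview is handled differently. Appendix 7 tells interviewers: "It is very important that you do not lead the patient with your questions or remarks". It lists acceptable non-leading probes and has the interviewer write down each symptom raised spontaneously before going through the remaining listed symptoms. Sections 3.3 and 4 require interviews to be recorded and transcribed.

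**The concern.** The app task exists to capture the patient's own account as it happens. If a participant is stuck and a researcher offers an example of what others might say, the example can supply the symptom, impact or feeling that comes back in the response. Once that response is coded like any transcript, with no marker of what preceded it, the researcher's idea and the patient's idea look the same. The app results then go into the conceptual model, and the qualitative analysis goes into the summary of content validity for the SNOT-22 and the VAS items. A sponsor asked to show that a concept came from patients would want to trace it to an unprompted statement. For app content the plan does not ensure that this can be done.

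**Working it through.** The plan states no figure on this point and no hypothesis is tested, so the check is a comparison of the texts, followed by simple counts.

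**Safeguards, interview against app**

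| Safeguard | Interview | App task |
|---|---|---|
| Rule against leading | Appendix 7, role of the interviewer | None found |
| Listed neutral probes | Appendix 7, same section | None found |
| Note of spontaneous mentions | Appendix 7, symptom list | None found |
| Prompt kept with the answer | Recording and transcript (sections 3.3 and 4) | Dashboard data stored (section 3.3); nothing stated for email or telephone contact during the task |
| Prompted/spontaneous code in analysis | None stated in section 4 | None stated in section 4 |

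The fourth row matters most. Section 4 does provide for recording and transcribing the feedback call held after the app task. It says nothing comparable about telephone or email help given while the task is running.

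**Does the permission cover content, or only format?** The key words are "probes/examples if they are unsure of how to respond to a task/question". Taken alone, they could mean only whether to send a video, a photograph or text. Two things point wider. The stated aim of the contact is thoroughness, which concerns what is said. Section 3.3 also describes interview probing as a way to raise matters the participant has not mentioned, so a probe in this protocol can carry content. The text leaves both readings open, and nothing excludes the content reading.

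**How much data is exposed**

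- App participants among all participants: 10/30 = 33.3%; among US participants: 10/20 = 50%.
- One app participant as a share of any app count: 1/10 = 10%. This is the granularity of the count, not an estimate of bias.
- Participants who do the app before the interview (section 3.1): 5 of 10. Their interviews are 5/30 = 16.7% of all interviews and 5/20 = 25% of US interviews.

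**Two routes for the effect**

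1. Direct: a prompted response is coded as ordinary app content and enters the conceptual model.
2. Carry-over: an app-first participant adopts a term a researcher supplied and later uses it unprompted in the interview, where it is noted as spontaneous. This route reaches the CE data on which saturation is judged, for at most those five interviews.

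**The case against.** The strongest reply is that the main data source is itself heavily probed. Interviewers go through every symptom on a 27-item list that was not raised spontaneously, put set questions on sleep, emotional, social, work and financial impacts, and may devise their own probes. The table for ticking spontaneous mentions is optional, and section 4 sets no prompted/spontaneous code for interviews either. Concepts named by a researcher and confirmed by a patient are thus normal input to this study. The five participants who do the app after the interview have already been taken through that list. All this stands, and it limits the harm. It does not remove the difference: in the interview the researcher's words are on the transcript, so a reader can see who spoke first.

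It is also fair that examples may mean response format, at least in part, that stored dashboard data may preserve in-app messages, and that the team managing the app also does the coding and may know who was helped. The gap in the record is therefore firm only for email and telephone contact.

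A reader might infer that extra tasks are given to participants who struggle, so that app content is not comparable across the ten. The documents do not support this. Adding tasks is a general dashboard function, not tied to anyone being unsure and not said to be used for selected individuals. Nor should one infer that help goes mainly to those with least to say: the stated trigger is being unsure how to respond.

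**Conclusion.** The point holds as a permitted risk of modest size. The wording allows researchers to supply content, withholds the interview's safeguards from the app, and leaves email and telephone prompts without a stated place in the record, while coding the responses as if they were transcripts.

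The size is limited for three reasons. Section 2.2 presents the app data as a supplement to the CE interviews; section 4 assesses saturation on those interviews alone; and there are no endpoints. A reader might want to state by what percentage a concept's frequency would be inflated. No such figure can be defended: the documents do not say how many participants will need help, what examples they would receive, or how often they would repeat them. Section 4 also rules out quantitative analysis of mention counts, although the counts may be reported.

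The conclusion assumes that at least some probes or examples would carry content. If only format help was intended, the change below simply makes that clear.

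**What to change.** 1. In the synopsis Limitations and its repeat in section 5, replace the permission for probes and examples, and put the same rule in section 3.3 where contact through the dashboard is described. Suggested text: *Contact during the app task is limited to reminders, help with using the app and choosing a response format, and neutral non-leading probes as listed in the interview guide. No example symptoms, impacts or feelings are supplied.* All three places need the change, or the protocol will contradict itself.
2. In section 3.3, require every researcher prompt, by any channel, to be stored with the response that followed it.
3. In section 4, add an Atlas.Ti attribute marking content first given after an individual researcher follow-up as prompted. The standard task wording does not count as a prompt for this purpose, since every app response follows a task. The report can then identify concepts that rest only on prompted app content.

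The cost is a wording change in three places, a log of prompts and one code attribute. Some responses may be shorter because example answers are no longer available.
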